Specific objectives:

1. To evaluate the effect of vitamin C, vitamin D and zinc supplementation on metabolic control (plasma glucose, HOMA, Hb1Ac and lipid profile).
2. To analyse the effect of vitamin C, vitamin D and zinc supplementation on inflammatory and immune biomarkers.
3. To analyse the effect of vitamin C, vitamin D and zinc supplementation on oxidative stress and antioxidant profile.
4. To evaluate the effect of vitamin C, vitamin D and zinc supplementation on gut microbiota.

4. Methods

Study design

Clinical trial randomized, prospective, placebo-controlled, double blinded, comparing two groups of patients with type 2 diabetes mellitus in the State of Mexico.

According to the calculation of the sample size, we will include 120 adults with type 2 diabetes mellitus selected from the outpatient preventive medicine offices of health centres in the State of Mexico who will be divided in two groups: supplement and placebo (60 per group). After having been invited to participate and obtaining the informed consent, study subjects will be evaluated for dietary information, as well as biochemical biomarkers of metabolic control, anthropometric, immune and inflammatory markers, gut microbiota and oxidative stress, before beginning the trial, and after 12 and 24 weeks of supplementation. They will have a monthly follow-up visit for evaluation of adherence and adverse effects, as well as delivery of the supplement.

Study groups

Subjects will be randomly allocated to a supplementation with 1000 mg vitamin C, 400 IU vitamin D and 10 mg of zinc or placebo group, during 24 weeks. Subjects and researchers will be blinded to the supplement or placebo in order to guarantee double-blinding.

Sample size calculations:

Based on a previous study done by this same research group (*Nutrients* 2017, 9, 573; doi:10.3390/nu9060573), we calculated the sample size with the data on the effect of a

6-month *n*-3 fatty acid supplementation trial on glucose concentrations of group of subjects with type 2 diabetes mellitus,

The calculations were done with the following formula:

$$N = \frac{(2 \times s^2)(Z\alpha + Z\beta)^2}{d^2}$$

Where: $Z_{\alpha/2} = 1.96$, $Z_{\beta} = 0.84$, $s = 68.9$ mg/dL and $d = 40$ mg/dL

Thus:

$$N = \frac{(2 \times 4747.21)(1.96 + 0.84)^2}{40^2} = 46 \approx 50 \text{ subjects}$$

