Accounting for a 20% loss at follow-up, we added 10 subjects, resulting in 60 subjects per group. This sample size guarantees that we should be able to observe significant differences in all the other indicators we will measure.

The following criteria will be used for the selection of the study sample:

Inclusion criteria

- Between 25 and 55 years of age, as this is the age in which type 2 diabetes mellitus is more prevalent and there is less probability of encountering multiple diseases in the same subjects
- Both sexes
- Outpatients
- BIM ≥ 25

Exclusion criteria

- Without any other chronic disease (cancer, cardiovascular diseases, arthritis and Alzheimer's).
- Severe renal insufficiency.
- Nephrolithiasis or history of nephrolithiasis.
- Hyperoxaluria.
- Hemochromatosis.
- Hypercalcaemia.
- Hypervitaminosis D.
- Using insulin.
- Be taking drugs such as desferrioxamine, iron, cyclosporine, indinavir (protease inhibitors), warfarin, thiazide diuretic, orlistat, ion exchange resins (e.g. cholestyramine, laxatives (e.g. mineral oil, senna), vitamin d analogues (e.g. ergocalciferol, calcitriol, and topical calcipotriene), tetracycline antibiotics, quinolone antibiotics, penicillamine, biphosphonates, levothyroxine, eltrombopag).
- Patients with hypersensitivity to any of the active substance(s) or to any of the excipients.
- Hypersensitivity to the by-products including honey, conifers, poplars, Peru balsam, and salicylate.

- Intake of probiotics or supplemental vitamin or mineral (vitamin D, C, zinc or calcium) for 4 weeks before the beginning of the study.
- Smoking and alcohol consumption (> 40 gr/ day for men and 25 gr/ day for women).
- Pregnant or lactating.
- Whose parents or grandparents are/were immigrant or of native origin.

Measurements.

Subjects will be selected from the outpatient preventive medicine offices of health centres in the State of Mexico. After having been invited to participate and obtaining their informed consent, study subjects will be evaluated for dietary information, as well as biochemical, anthropometric, immune and inflammatory markers, as well as intestinal microbiota before beginning the trial, at 12 and 24 weeks of supplementation.

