A qualified physician will do a complete clinical history. Subjects will be requested to fill-out the Diabetes 39 quality of life questionnaire (validated in Mexico), at baseline and at the end of the study. Questions on frequency of respiratory, urinary and gastrointestinal infections as well as on perception with respect to the supplement will be included.

A standardized nutritionist will evaluate Dietary History, a food-frequency questionnaire (FFQ), as well as three 24-hour food registry of non-consecutive days including one from the weekend. The FFQ will be analysed in DIAL software to evaluate dietary intake of vitamin C, vitamin D and zinc. Anthropometric evaluations will be done by a standardized nutritionist; weight will be measured with a 1631 TANITA™ portable electronic scale, stature with a 1013522 SECA™ portable stadiometer, for the calculation of BMI.

Faecal samples will be obtained for evaluation of intestinal microbiota. We will proceed to isolate and characterize the bacteria obtained from the faecal samples with two enriched culture media for the purification of the most representative and abundant strains. The isolated strains will be classified in morphological groups according to their macroscopic characteristics of size, form, surface, consistency and color. A selection of 40% of the representative samples from each morphologic group will be typified by the RFLP method. We will obtain biomass and extract DNA, for amplification of the 16S rRNA gene, with an enzymatic genotyping and strain grouping. The strains will be grouped to compare their diversity; the results of the groups will be compared to appreciate the differences between the type and number of strains obtained.

At each sampling date, a venous blood sample of 8.5 mL will be obtained after a 12 hour fast for the measurement of vitamin C (HPLC); zinc (Atomic Absorption Spectrometry); vitamin D and Vitamin D binding protein (ELISA); plasma glucose; triacylglycerides; total cholesterol; HDL and LDL-cholesterol and Hb1Ac (Automated Selectra equipment with Randox™ reactants); pro inflammatory cytokines (TNF α , IFN- γ , IL-1 β) and anti-inflammatory cytokines (IL4, IL-6, IL10, TGF- β), apolipoproteins A and B, C-reactive protein, V-CAM, I-CAM, complement proteins C-3 and C-4, insulin, adiponectin, resistin and leptin will be analysed with multiplex technology (Milliplex Luminex™). Additionally we will measure biomarkers of oxidative stress and

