A specific database will be designed in SPSS 19.0®. Data will be described with means and standard deviations or frequencies and percentages depending on the type of data. We will undertake a normality analysis, after which differences between groups will be analysed by parametric or non-parametric statistical tests. A multiple regression analysis will be run in order to establish interactions between variables.

References

Barengolts E. Vitamin D and prebiotics may benefit the intestinal microbacteria and improve glucose homeostasis in prediabetes and type 2 diabetes. *Endocr Pract* 2013; **19**(3): 497-510. doi: 10.4158/EP12263.RA.

Crook M. Type 2 diabetes mellitus: a disease of the innate immune system? An update. *Diabetic Medicine*. 2003; **21**:203-7.

Diabetes Public Health. From Data to Policy: Oxford University Press; 2011

Encuesta Nacional de Salud y Nutrición 2012. http://www.insp.mx/ensanut/resultados_ensanut.html.

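### The plan claims that 60 per group secures significant differences in every other indicator, but the only calculation is for glucose (0.58 SD, 80% power)

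*Combined protocol and SAP*

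**What the plan says.** The Sample size calculations part of section 4 (Methods) takes its inputs from the group's earlier "fatty acid supplementation trial on glucose concentrations of group of subjects with type 2 diabetes mellitus". It uses an SD of 68.9 mg/dL, a difference of 40 mg/dL and Z values of 1.96 and 0.84. The result is 46 per group, rounded up to 50. The plan then states: "Accounting for a 20% loss at follow-up, we added 10 subjects, resulting in 60 subjects per group".

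The next sentence extends the result to everything else: "This sample size guarantees that we should be able to observe significant differences in all the other indicators we will measure".

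The other indicators are many. The Measurements section lists HbA1c, lipids, seven cytokines and six oxidative-stress and antioxidant assays. A further group is described as "C-reactive protein, V-CAM, I-CAM, complement proteins C-3 and C-4, insulin, adiponectin, resistin and leptin will be analysed with multiplex technology". For the microbiota, "the results of the groups will be compared to appreciate the differences between the type and number of strains obtained". The Data Collection and Statistical Analysis section says only that "differences between groups will be analysed by parametric or non-parametric statistical tests", followed by a multiple regression. It makes no statement about power.

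**The concern.** Power depends on each outcome's own true difference and SD. A calculation for glucose says nothing about a cytokine or a strain count unless the plan argues that their standardised effects are at least as large, and it does not. Even for glucose, 80% power leaves about a one-in-five chance of missing the assumed effect.

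This sentence is the only statement of adequacy for objectives 2, 3 and 4 (inflammatory and immune markers, oxidative stress, microbiota) and for the rest of objective 1. The plan is also silent on how null results will be interpreted. If the protocol says detection is assured, a non-significant result invites the reading that there is no effect, when the trial may simply have been too small to show one.

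**Working it through.** **Inputs from the plan.** SD 68.9 mg/dL, difference 40 mg/dL, Z values 1.96 and 0.84 (two-sided 5%, 80% power), 60 per group, 20% loss.

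**Reproducing the plan's figure.** N = 2 × 68.9² × (1.96 + 0.84)² / 40² = 2 × 4747.21 × 7.84 / 1600 = 46.52 per group. The plan states 46; rounding up gives 47. The difference is immaterial.

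**Standardised effect.** 40 / 68.9 = 0.58 SD.

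**Evaluable number.** 60 × 0.8 = 48 per group. This is slightly below the plan's 50 but above the 47 required.

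**Power for glucose.** For a two-sample t-test, power is the probability that a non-central t variable with 2n − 2 degrees of freedom and non-centrality δ√(n/2) exceeds the two-sided 5% critical value in absolute size. With n = 48, the non-centrality is 0.5806 × √24 = 2.84 and power is 80.4%. With n = 60 (no loss) it is 88.4%.

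**Power at other effects.** The plan gives no effect for any other outcome. The values of δ from 0.2 to 0.5 SD are therefore assumptions, chosen to show what lies below the glucose target.

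| True difference | Power, 48 per group | Power, 60 per group | Evaluable per group for 80% power |
|---|---|---|---|
| 0.5 SD | 68% | 78% | 64 |
| 0.4 SD | 49% | 58% | 100 |
| 0.3 SD | 31% | 37% | 176 |
| 0.2 SD | 16% | 19% | 394 |

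The difference detectable with 80% power is 0.578 SD at 48 per group (0.578 × 68.9 = 39.8 mg/dL on the glucose scale) and 0.516 SD at 60 per group. A normal approximation in place of the t-test moves these figures by about one percentage point of power or 0.01 SD.

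**Would baseline adjustment rescue the claim?** The plan does not specify it. If it were used, the threshold would be multiplied by √(1 − r²), where r is the correlation between baseline and follow-up. The r values are assumptions.

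- r = 0.5: 0.578 × 0.866 = 0.50 SD; power at 0.3 SD is 39%.
- r = 0.7: 0.578 × 0.714 = 0.41 SD; power at 0.3 SD is 53%.

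The threshold falls, but detection is still not assured.

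**The case against.** Four points can be made for the plan.

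- **The wording is softer than an outright guarantee.** The sentence says the investigators should be able to see differences. It still asserts adequate power for every indicator without support.
- **The assumed range is one-sided.** All the effects in the table lie below 0.58 SD. At 48 per group, power is 83% at 0.6 SD, 92% at 0.7 and 97% at 0.8. This stands: the document cannot tell us which range applies, so the table shows that the claim is unproven, not that the trial is underpowered for any named marker.
- **The harm is inferred.** No passage says that a null result will be read as no effect, and the sentence drives no sample size, test or decision rule. That is true, and it limits the severity. It does not make the sentence correct.
- **The 0.58 SD figure is itself a per-test, uncorrected figure.** Many markers are measured, at 12 and 24 weeks, with no stated approach to multiplicity. As an illustration, a Bonferroni correction over 30 tests (an assumed number) would raise the 80%-power threshold at 48 per group to about 0.84 SD. This stands, and the replacement text should carry the qualification.

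One limit also applies to the check on glucose. Its arithmetic reproduces, but the 68.9 and 40 mg/dL inputs come from a trial of a different supplement and cannot be verified from this document.

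**Conclusion.** The concern holds. The plan claims for every other indicator a property that it shows for glucose alone. With 48 evaluable per group and an unadjusted two-sided 5% t-test, 80% power needs a true difference of about 0.58 SD; at an assumed 0.3 SD power is about 31%, and at 0.4 SD about 49%. Full retention lowers the threshold only to 0.52 SD.

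This is an unsupported statement, not an error in the sample size. The size for glucose stands on the plan's own inputs, and any continuous outcome with a true effect of 0.58 SD or more would have at least 80% power under the same test. The sentence should be corrected because it is the only support for the adequacy of most of the stated objectives.

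**What to change.** Delete the sentence and put in its place:

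> With 60 randomised per group and 20% loss (48 evaluable), the trial has about 80% power (two-sided 5%) for a 40 mg/dL difference in glucose (SD 68.9 mg/dL). The trial was not sized for the other indicators. For a continuous outcome compared by an unadjusted t-test, 80% power requires a true difference of about 0.58 SD; this figure is per test, without correction for multiplicity, and does not apply to counts, frequencies or other tests. These outcomes will be reported with 95% confidence intervals, and a non-significant result will not be taken as evidence of no effect.

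The exclusion of counts and frequencies matters for the infection questions and for the type and number of strains. How the outcomes are ranked is for the sponsor to decide.

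The cost is small: no extra patients and no change to randomisation, sample size or tests. The stated power for the other indicators becomes less favourable, and the plan takes on a commitment to report confidence intervals for them.

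### The first exclusion criterion is inverted as written: it excludes patients with no other chronic disease and does not itself exclude those with the listed diseases

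*Combined protocol and SAP*

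**What the plan says.** Section 4 (Methods) introduces the two eligibility lists as operative rules: "The following criteria will be used for the selection of the study sample". The first bullet under Exclusion criteria begins "Without any other chronic disease (cancer, cardiovascular diseases, arthritis", and its parenthesis ends with Alzheimer's disease. Neighbouring bullets in the same list include "Severe renal insufficiency" and "Nephrolithiasis or history of nephrolithiasis".

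The inclusion list covers age, sex, outpatient status and body mass index. It contains no comorbidity rule. Comorbidity appears there only in the reason for the age range of 25 to 55 years, part of which is that "there is less probability of encountering multiple diseases in the same subjects".

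**The concern.** An exclusion list works by naming states whose presence keeps a patient out. A bullet that begins with a negation reverses that. Here the state that keeps a patient out is having no other chronic disease, which is the opposite of what the age rationale suggests was wanted.

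The line is an eligibility rule, so it is what screening staff, an ethics committee, a monitor and a reader of the results would consult to learn who belongs in the trial. Hypothesis 1, hypothesis 4 and specific objectives 2 and 3 concern cytokines, other inflammatory and immune markers, and oxidative stress. If the listed diseases shift those markers, the comorbidity make-up of the sample affects both what the results describe and how variable they are. The Data Collection and Statistical Analysis section names no comorbidity variable for stratification or adjustment, so the plan relies on the eligibility criteria alone to control this.

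**Working it through.** No formula applies, so the check sets the texts side by side.

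**1. The bullet under its heading.** Take three patients who meet every other criterion:

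| Patient | Literal reading of the bullet | Reading by apparent intent |
|---|---|---|
| Type 2 diabetes only | excluded | not excluded |
| Type 2 diabetes plus one of the four listed diseases | not excluded by this bullet | excluded |
| Type 2 diabetes plus an unlisted chronic disease | unclear | unclear |

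The first two rows reverse between the readings. The third is unclear under both, because the text does not say whether the four diseases are the full list or examples.

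**2. The rest of the exclusion list.** There are 15 bullets. The other 14 all name something whose presence excludes: a disease or metabolic state, use of insulin or of named drugs, hypersensitivity, recent supplement intake, smoking or alcohol, pregnancy or lactation, family origin. Only the first is negated. A reader who applies the convention of the other 14 to it gets the reversed rule.

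**3. The inclusion list.** The age criterion is partly justified by a lower chance of multiple disease. That is a reason for an age range and not itself a comorbidity rule, so the conflict is one of purpose, not of one rule against another. Even so, a literal first bullet would select for the state that the age range is meant to make less likely.

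**4. Anything elsewhere that settles it.** Study design, Measurements, Follow-up, and Data Collection and Statistical Analysis contain no other general comorbidity rule. Measurements has a physician take a full clinical history but gives that step no eligibility function. Some exclusion bullets cover particular conditions (for example severe renal insufficiency and hemochromatosis). The drug bullet would remove some patients with cardiovascular disease, such as those on warfarin or a thiazide diuretic. No bullet except the first addresses cancer, cardiovascular disease, arthritis or Alzheimer's disease as such.

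**5. Effect on the sample size.** The criterion enters no calculation. The plan's formula with its own inputs gives 2 × 68.9² × (1.96 + 0.84)² / 40² = 2 × 4747.21 × 7.84 / 1600 = 46.5 per group, against the stated 46, and rewording the bullet does not change it. The formula scales with s², so a more heterogeneous sample would need more patients if s rose. The documents give neither a comorbidity prevalence nor standard deviations by comorbidity, so no size can be attached to this.

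**The case against.** The strongest case on the other side is that the intent is plain. The age rationale and the 14 other bullets point the same way, and the line reads as an inclusion criterion placed under the wrong heading. With a physician taking a full history, it is implausible that every comorbidity-free patient would be turned away. On that view this is a wording slip. It stands as an account of how the line arose, but it does not make the rule correct: the protocol is what screening and deviations are judged against, and nothing else in it states the intended rule.

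Four stronger readings are tempting, and the documents do not support them.

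- **Eligibility is reversed for every screened patient.** It is not. Anyone who fails on age, body mass index, insulin use, a listed drug or another criterion is ineligible under either reading.
- **An audit against the written rule would flag every enrolled participant.** This cannot be derived. If the four diseases are only examples, a participant with an unlisted chronic condition would comply with the literal rule, and no prevalence is given.
- **The wrong patients were or will be enrolled.** No screening form or enrolment record is among the documents, so nothing shows literal application.
- **The treatment comparison is biased.** Allocation is random and double-blind. Comorbidity in the sample would change who is studied and possibly the variability of outcomes, without systematically favouring one arm.

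It is also fair to say that the plan does not itself state that all four diseases alter the trial's markers. Its background ties oxidative stress to vascular damage in diabetes, but makes no such statement for arthritis or cancer.

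**Conclusion.** The point holds in a limited form: an operative eligibility rule is wrong as written and needs correcting. Followed exactly, it would reverse the comorbidity selection among patients who satisfy the other criteria, in a trial where inflammatory and oxidative-stress markers are among the outcomes. If staff follow the apparent intent, the defect is confined to the record. The sample size and the validity of the randomised comparison are untouched either way.

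The conclusion about wording rests on the text alone. The conclusion about consequences rests on two assumptions: that the line might be applied or reported as it stands, and that the listed diseases affect the measured markers. Neither is demonstrated in the documents. The most likely explanation is a drafting error, not a deliberate design decision.

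**What to change.** Reconcile the bullet with the age rationale in one of two ways: reword it under Exclusion criteria as the presence of another chronic disease, or move the existing phrase to the inclusion list. In the same edit, state whether the four named diseases are the complete list or examples. Without that, a broad reading of any other chronic disease could exclude many more patients than a narrow one, and rewording alone would leave the population undefined.

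Use the identical wording in the screening form and in the report of the trial. If enrolment has begun, document which reading was applied.

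The cost is one line of protocol text. No sample-size, randomisation or analysis provision changes. The one substantive decision is whether the list is closed or open, which the sponsor has to make.

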It has been shown that zinc supplementation may reduce glucose and HbA1c concentrations in diabetic subjects, contributing to an adequate metabolic control of the disease. High levels of serum zinc have been associated to lower risk of CVD in diabetic patients. Zinc supplementation has been suggested as an additional treatment for metabolic control in type 2 diabetic patients as it promotes insulin signalling. Inflammatory cytokines in type 2 diabetes mellitus are associated to zinc metabolism by zinc transporter and metallothionein gene expression.

Gut microbiota

The adult intestinal microbiota is composed of hundreds to thousands of species, dominated by the Bacteroidetes and Firmicutes phyla. This ecosystem is different and unique, since it includes many species that do not exist in another part of nature, which indicates powerful selective mechanisms that have generated a coevolution of the host with its intestinal microbial symbionts (commensal and mutualists). The adult intestinal microbiota is also partially stable, composed of approximately 40 bacterial species (representing 75% of the intestinal microbiota in terms of abundance).

In recent years, much attention has been given to the microbial community within the human body and its association to the immune system as well as to the development of chronic diseases such as obesity and type 2 diabetes mellitus. There are many factors involved in the health of this microbiota, such as genetics, environment, use of medications and particularly diet. Some types of microorganisms in the microbiota may promote inflammation increasing the risk for chronic diseases. Increased microbial diversity has been associated to decreased inflammation. Dysbiosis of gut microbiota has been associated to insulin resistance and glucose homeostasis as well as low-grade inflammation. It has been identified that the effect on insulin metabolism is through the regulation of insulin signalling molecules such as GLP-1 and PYY, which reduce insulin resistance and improvement of β -cell function.

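### Gut microbiota is an objective, but the plan specifies no antibiotic look-back or antibiotic record around the faecal samples

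*Combined protocol and SAP*

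**What the plan says.** **The outcome.** The fourth specific objective (section 3) is "To evaluate the effect of vitamin C, vitamin D and zinc supplementation on gut microbiota", and hypothesis 3 (section 2) expects a better microbiota profile after supplementation. Section 4, Measurements, schedules the assessment: "as well as intestinal microbiota before beginning the trial, at 12 and 24 weeks of supplementation". The method is culture followed by strain typing, and "the results of the groups will be compared to appreciate the differences between the type and number of strains obtained".

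**What the plan says affects it.** The background subsection on gut microbiota lists influences "such as genetics, environment, use of medications and particularly diet".

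**The drug exclusion (section 4, Exclusion criteria).** It opens "Be taking drugs such as desferrioxamine, iron, cyclosporine" and later names "tetracycline antibiotics, quinolone antibiotics". It concerns current use, and the drugs are given as examples.

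**The look-back (same section).** A separate item excludes "Intake of probiotics or supplemental vitamin or mineral (vitamin D, C, zinc or calcium) for 4 weeks before the beginning of the study". Antibiotics are not part of it.

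**What is recorded.** Section 4, Measurements, provides for a clinical history by a physician and "Questions on frequency of respiratory, urinary and gastrointestinal infections". The monthly visits cover adherence, adverse effects and delivery of the supplement. Follow-up provides for adverse event collection from the first day of supplementation. None of these names antibiotic use or its dates. Data Collection and Statistical Analysis does not mention it.

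**The concern.** Antibacterial drugs act directly on what is measured here, the kinds and numbers of bacteria that can be cultured from stool. As written, a patient who finished an antibiotic course a few days before the baseline sample is eligible and is sampled. That holds even for the two named classes, because the criterion looks only at current use. Nothing addresses courses taken shortly before the week-12 or week-24 sample. The plan itself says that these patients face a raised risk of some infections (section 2), so such courses are foreseeable.

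Two things are at stake, both confined to the microbiota objective. The first is precision: exposed samples add variation that a look-back could remove at baseline and a record could explain later. The second is interpretation: if the arms differ, nobody could show whether the difference runs through antibiotic use, because the dates needed to examine this would not have been collected by design.

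**Working it through.** **1. Side-by-side reading**

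| Item | Probiotics, vitamins, minerals | Tetracyclines, quinolones | Other antibiotics |
|---|---|---|---|
| Named at entry | yes | yes, current use | no (the list is open) |
| Look-back before baseline | 4 weeks | none | none |
| Record specified before weeks 12 and 24 | not examined here | none | none |
| Analysis rule | not examined here | none | none |

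**2. The base for the arithmetic.** The plan has no sample size for microbiota. Its only calculation is for glucose: 2 × 4747.21 × (1.96 + 0.84)² / 40² = 46.5 per group. The plan states this as 46, rounds it to 50, and adds 10 for 20% loss to reach 60. Completers expected per group: 60 × (1 − 0.20) = 48.

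**3. Noise from exposed samples.** The documents give no rate of antibiotic use, no microbiota SD and no size of antibiotic effect. Assumptions:
- A share f of samples is exposed, with f from 0.05 to 0.20.
- Exposure shifts the outcome by δ, from 1 to 2 SD.
- Exposure is unrelated to arm.
- The outcome can be summarised as one roughly continuous measure. The plan names only type and number of strains, so this is a simplification.

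Formulas: variance factor = 1 + f(1 − f)δ²; effective n = 48 / factor; detectable difference = 2.8 × √(2 / effective n), using the plan's 1.96 + 0.84 = 2.8.

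| f | δ (SD) | Variance factor | Effective n per group | Detectable difference (SD) |
|---|---|---|---|---|
| 0 | – | 1.00 | 48 | 0.57 |
| 0.05 | 1 | 1.048 | 45.8 | 0.59 |
| 0.10 | 2 | 1.36 | 35.3 | 0.67 |
| 0.20 | 2 | 1.64 | 29.3 | 0.73 |

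Chance imbalance between arms is already in these figures and should not be added to them.

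**4. How extreme is the upper end?** Twenty-four weeks contain 24 / 4 = 6 four-week windows. If 20% of patients were exposed in every window, that is 6 × 0.20 = 1.2 exposed windows per patient. At 10% it is 0.6, and at 5% it is 0.3. The 20% case is demanding for outpatients aged 25 to 55 selected against other chronic disease.

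**5. Cost in numbers of setting exposed samples aside.** With 10% removed, 48 × 0.90 = 43.2 remain and the detectable difference is 0.60 SD. With 20% removed, 48 × 0.80 = 38.4 remain and it is 0.64 SD.

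**The case against.** **The list is open, and it was probably not written for the microbiota.** The two classes stand beside drugs such as penicillamine, iron and levothyroxine, which suggests concern about interactions with the supplement. An investigator could read the examples as covering other antibiotics. This stands, so a reader who infers that every other antibiotic is permitted at entry goes beyond the text. What remains is that no rule, look-back or record is stated for the faecal samples, and investigators could apply the open list differently.

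**Antibiotic courses would surface anyway.** A reader might infer that they go unrecorded. The documents do not show that: the clinical history, the infection questions, monthly contact and adverse event reports may each capture some. But none specifies drug and dates, and dates relative to each stool sample are what an analysis needs.

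**Randomisation deals with it.** A reader might infer that the microbiota comparison is confounded. It is not. In a randomised double-blind trial, later antibiotic use is also balanced in expectation unless the supplement itself changes infections or prescribing. If it does, antibiotic use is a consequence of treatment, and comparing all samples still estimates the total effect, which is what objective 4 asks for. Nor do the infection questions make infection frequency a trial hypothesis; no objective concerns it. The objection therefore defeats a claim of bias. It does not remove the noise or the problem of interpretation.

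**The size is assumed throughout.** This is true, and at the low end the loss is about 2 of 48 per group, which is negligible.

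**Conclusion.** The gap is real and limited. An outcome based on cultured strains is planned with no antibiotic look-back before baseline and no specified antibiotic record before the later samples, although the plan applies a 4-week look-back to probiotics and names medication use as an influence.

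The consequence is avoidable noise and chance imbalance, plus an inability to say whether any difference between arms runs through antibiotic use. It is not a biased estimate of the total effect. Under assumed exposure of 5–20% and an assumed shift of 1–2 SD, variance rises by about 5–64%, and effective size falls from 48 to between about 46 and 29 per group. The lower figure needs both extremes together. None of these inputs comes from the documents.

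The glucose sample size and the other three objectives are unaffected. This is a cheap improvement to one objective.

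**What to change.** 1. **Baseline timing.** Extend the existing 4-week look-back to systemic antibiotics, for the timing of the baseline faecal sample only. Postpone the sample, and with it the start of supplementation; do not restrict treatment. The 4 weeks are borrowed from the probiotic item for consistency, and the documents do not justify that length for antibiotics, so the investigators should confirm it. Whether to widen the exclusion list is also for them.
2. **Record.** At weeks 12 and 24, ask about any antibiotic taken in the 4 weeks before the sample, with drug and dates. Report use by arm and visit.
3. **Analysis.** Keep the comparison of all samples as the main microbiota analysis. Prespecify a supportive sensitivity analysis by antibiotic exposure. Label it as conditioning on an event after randomisation: if the supplement changes infections, setting exposed samples aside can itself introduce selection bias, so this analysis must not replace the main one.

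Cost: one line in the criteria, one question per sampling visit, a short addition to the analysis section, and a few baseline samples delayed by up to 4 weeks.
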